2.1.2 Secondary Objectives

- Determine the PFS rate at 1 year- by both RECIST and irRECIST of nivolumab in patients with treatment naïve ccRCC based on the PD1- Blockade Durable Response Predictive (PRP) biomarker model developed in the DFHCC Kidney Cancer SPORE
- Determine the objective response rate (CR/PR=ORR), the ORR based on PDL1 expression and the PRP model, and duration of response for nivolumab in patients with treatment naïve ccRCC
- Determine the response rate of combined nivolumab and ipilimumab therapy at the time of nivolumab failure (or lack of response at 1 year)
- Determine the clinical activity (CR, PR and SD) and PFS at 1 year of nivolumab in patients with treatment naïve nccRCC
- Assess the toxicity of nivolumab monotherapy in patients with treatment naïve cc or nccRCC

2.1.3 Correlative/Exploratory Objectives

- Explore novel potential predictive biomarkers for patients with treatment naïve ccRCC and nccRCC
- Explore the mechanisms of innate and acquired resistance to nivolumab therapy in treatment naïve patients with ccRCC
- Identify biomarkers associated with response to nivolumab + ipilimumab in patients whose disease has not responded or progressed on nivolumab monotherapy

2.2 Endpoints

2.2.1 Primary Endpoint

- PFS is defined as the time from Day 1 of treatment until the criteria for disease progression is met as defined by RECIST 1.1 or death as a result of any cause.
- The primary focus of this trial will be in the evaluation of PD-L1 expression levels to predict outcome. We expect that about 45% (or 54 expected) patients will have 0% PD-L1 and roughly 15% (or 18 expected) patients will express PD-L1 > 20%, which, given the sample size of 120 ccRCC patients provides 90% power using a 0.05 level two-sided test to test the hypothesis that PD-L1 >20% will be associated with significantly improved 1-year PFS rate for patients treated with PD-1 blockade (55% vs 13% taken as a binomial quantity).

2.2.2 Secondary Endpoints

- Apply the PRP model, developed in the DF/HCC Kidney SPORE Project 4, to assign each patient a probability of having PFS > 1 year.
- The endpoint for Part B (addition of ipilimumab) will be objective response (CR or PR) taking as baseline tumor measurements at the patient's start of Part B.
- An expected cohort of 40 nccRCC patients will be enrolled in the trial and analyzed separately for evidence of anti-tumor activity, principally focusing on objective response rate (CR or PR).
- Toxicity by CTCAE criteria of nivolumab monotherapy in treatment naïve patients with cc and nccRCC.

2.2.3 Correlative Endpoint

- Additional correlative studies will be performed in order to identify predictors of response and resistance.

3. ELIGIBILITY CRITERIA

3.1 Inclusion Criteria-Part A

Subject must meet all of the following applicable inclusion criteria to participate in this study:

1. Patients must have histologically confirmed advanced RCC (any histology). Collecting duct tumors and tumors originating from the renal pelvis or upper urinary tract are considered of urothelial origin and are excluded from this protocol.
2. Patients must have at least one measurable site of disease, per RECIST 1.1, that has not been previously irradiated. If the patient has had previous radiation to the marker lesion(s), there must be evidence of progression since the radiation.
3. Archival tissue of a metastatic lesion obtained within 1 year prior to study registration (within 4 weeks preferred) and tumor tissue from nephrectomy is required if available. In addition to archival tissue of a metastatic lesion and nephrectomy, patients must have at least one site of disease (not including bone metastases) accessible for biopsy. If biopsy/resection of a new lesion or primary tumor and slow freezing of fresh tissue for single cell RNAseq study (as specified in the CLM) is not feasible, the subject is not eligible for the study. All biopsies must be core needle or excisional. Fine needle aspirate is not acceptable. **NOTE:** The tissue collected from a surgical resection or multiple core biopsies of either a metastatic lesion or primary tumor for the slow freezing of fresh tissue after the patient has signed consent for the study could also be used for collecting the FFPE specimens.
4. ECOG performance status 0-2.
5. Age \geq 18 years.
6. Have signed the current approved informed consent form.

7. Patients must have adequate organ function within 14 days prior to study entry as evidenced by screening laboratory values that must meet the following criteria:

System	Laboratory Value
Hematological	
White blood cell (WBC)	$\geq 2000/\mu\text{L}$
Absolute Neutrophil Count (ANC)	$\geq 1500/\mu\text{L}$
Platelets (Plt)	$\geq 100 \times 10^3/\mu\text{L}$
Hemoglobin (Hgb)	$> 9.0 \text{ g/dL}$ (with or without transfusion)
Renal	
Serum Creatinine OR	$\leq 1.5 \times \text{ULN}$; if creatinine > 1.5 , subject must demonstrate CrCl outlined below.
Calculated or measured creatinine clearance ¹	$\geq 40 \text{ mL/min}$ using Cockcroft-Gault formula
Hepatic	
Bilirubin ²	$\leq 1.5 \times$ upper limit of normal (ULN)
Aspartate aminotransferase (AST)	$\leq 3 \times \text{ULN}$
Alanine aminotransferase (ALT)	$\leq 3 \times \text{ULN}$

1: Female CrCl = $(140 - \text{age in years}) \times \text{weight in kg} \times 0.85$

$72 \times \text{serum creatinine in mg/dL}$

Male CrCl = $(140 - \text{age in years}) \times \text{weight in kg} \times 1.00$

$72 \times \text{serum creatinine in mg/dL}$

2: Except subjects with Gilbert Syndrome, who can have total bilirubin $< 3.0 \text{ mg/dL}$

8. Patients should not have received prior systemic therapy for metastatic RCC. Prior radiotherapy must have been completed at least 2 weeks prior to the administration of study drug. Patients must be 2 weeks from prior major surgery and 1 week from pre-treatment biopsy. Prior systemic adjuvant therapy (excluding with PD1 or CTLA4 pathway blockers) is allowed if treatment completed > 12 months previously.

9. Women of childbearing potential (WOCBP) must use appropriate method(s) of contraception. WOCBP should use an adequate method to avoid pregnancy for 5 months after the last dose of study drug. **NOTE:** Contraception is not required for male participants.

10. Women of childbearing potential must have a negative serum or urine pregnancy test (minimum sensitivity 25 IU/L or equivalent units of HCG) during screening for registration purposes. This pregnancy test should be repeated within 24 hours prior to the start of nivolumab. **NOTE:** "Women of childbearing potential" is defined as any female who has experienced menarche and who has not undergone surgical sterilization (hysterectomy or bilateral oophorectomy) or who is not postmenopausal. Menopause is defined clinically as 12 months of amenorrhea in a woman over 45 in the absence of other biological or physiological causes. In addition, women under the age of 55 must have a documented serum follicle stimulating hormone (FSH) level less than 40 mIU/ml.

11. Women must not be breastfeeding.

12. Be willing and able to comply with this protocol.

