1.3.1 Non-Clinical Studies

Nivolumab has been shown to bind specifically to the human PD-1 receptor and not to related members of the CD28 family [8, 9]. Nivolumab inhibits the interaction of PD-1 with its ligands, PD-L1 and PD-L2, resulting in enhanced T-cell proliferation and interferon-gamma (IFN- γ) release in vitro [9-11]. Nivolumab binds with high affinity to activated human T-cells expressing cell surface PD-1 and to cynomolgus monkey PD-1. In a mixed lymphocyte reaction (MLR), nivolumab promoted a reproducible concentration-dependent enhancement of IFN- γ release [12]. In intravenous (IV) repeat-dose toxicology studies in cynomolgus monkeys, nivolumab was well tolerated at doses up to 50 mg/kg, administered weekly for 5 weeks, and at doses up to 50 mg/kg, administered twice weekly for 27 doses. While nivolumab alone was well tolerated in

cynomolgus monkeys, combination studies have highlighted the potential for enhanced toxicity when combined with other immunostimulatory agents [13]. In addition, an enhanced pre- and postnatal development (ePPND) study in pregnant cynomolgus monkeys with nivolumab was conducted [14]. Administration of nivolumab at up to 50 mg/kg 2QW was well tolerated by pregnant monkeys; however, nivolumab was determined to be a selective developmental toxicant when administered from the period of organogenesis to parturition at > 10 mg/kg). Specifically, increased developmental mortality (including late gestational fetal losses and extreme prematurity with associated neonatal mortality) was noted in the absence of overt maternal toxicity. There were no nivolumab-related changes in surviving infants tested throughout the 6-month postnatal period. Although the cause of these pregnancy failures was undetermined, nivolumab-related effects on pregnancy maintenance are consistent with the established role of PD-L1 in maintaining fetomaternal tolerance in mice [15].

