2. Hematology Labs should include CBC with differential (hemoglobin, hematocrit, white blood cells, platelets, neutrophils, lymphocytes, eosinophils and monocytes). Additional draws must be incorporated when monitoring recovery from any hematologic AE. Chemistry Labs should include albumin, BUN, creatinine, ALT, AST, bilirubin serum alkaline phosphatase, glucose, total protein, sodium, potassium, chloride, HCO₃, calcium. Labs should be performed on the day of treatment but may be drawn up to 72 hours before to ensure return of results prior to dosing.
3. Other labs to be drawn: amylase, lipase, LDH, direct bilirubin (only if total bilirubin is elevated), uric acid and CPK Day 1 of every Cycle during treatment. Thyroid function will be monitored Day 1 of each cycle during treatment. TSH will be monitored and T3 and T4 (free versus total) should be drawn at site investigators discretion. It is suggested that if TSH is elevated T3 and T4 values may be done. At screening, testing should be performed for hepatitis C antibody and HBs Ag utilizing local standard informed consent procedures prior to this laboratory collection. These tests could be repeated later during the course of the study if clinically indicated.
4. Women of child-bearing potential must have a negative serum or urine pregnancy test within 24 hours prior to treatment with nivolumab and again at crossover to Part B for screening purposes.

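### The FSH condition in the menopause definition (Section 3.1, item 10) sets an upper limit where confirming menopause needs a lower one, and it decides who is exempt from contraception and pregnancy testing

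*Combined protocol and SAP*

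**What the plan says.** Section 3.1 handles childbearing potential in three steps.

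- **Who is covered.** Item 10 counts as being of childbearing potential "any female who has experienced menarche and who has not undergone surgical sterilization (hysterectomy or bilateral oophorectomy) or who is not postmenopausal".
- **What menopause means.** The next sentence reads "Menopause is defined clinically as 12 months of amenorrhea in a woman over 45 in the absence of other biological or physiological causes".
- **What is added for younger women.** The item closes, as an additional requirement, with "women under the age of 55 must have a documented serum follicle stimulating hormone (FSH) level less than 40 mIU/ml".

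The safeguards depend on this status. Item 9 states "Women of childbearing potential (WOCBP) must use appropriate method(s) of contraception" and extends contraception to 5 months after the last dose. Item 10 states "Women of childbearing potential must have a negative serum or urine pregnancy test" at screening, with a repeat in the 24 hours before nivolumab starts. Footnote 4 of the study calendar (Section 7) repeats this, "Women of child-bearing potential must have a negative serum or urine pregnancy test within 24 hours prior to treatment with nivolumab", and asks for another test at crossover to Part B. Section 3.3, item 1 makes Part B candidates meet the Part A criteria again, so the same definition is applied a second time.

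Section 1.3.1 gives the reason for caution: in pregnant monkeys "nivolumab was determined to be a selective developmental toxicant when administered from the period of organogenesis to parturition", with late fetal losses and neonatal deaths.

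**The concern.** The FSH sentence directly follows the definition of menopause and applies only to women under 55. Its evident purpose is to confirm, in the age range where amenorrhea alone is less conclusive, that ovarian function has ceased. Cessation of ovarian function raises FSH, so confirmation calls for a value that is high enough. The text asks for a value that is low enough.

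If sites follow the sentence, the women whose FSH gives least support to menopause lose the contraception requirement and the pregnancy tests, and the women whose FSH supports menopause keep them. The second error costs some unnecessary tests and contraception. The first could expose a pregnancy to a drug that the protocol itself describes as a developmental toxicant.

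**Working it through.** The plan gives no numerical result to reproduce here. The check is whether the rule, followed as written, gives the classification it is meant to give.

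**Inputs**

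- Menopause sentence (item 10): amenorrhea for a year, age over 45, no other cause. Call this condition A.
- FSH sentence (item 10): for women under 55, FSH below 40 mIU/ml. Call this condition F.
- Childbearing-potential sentence (item 10): past menarche, and not sterilised *or* not postmenopausal.
- Safeguards (items 9 and 10; calendar footnote 4): required only of women of childbearing potential.
- Assumption from basic physiology: FSH rises when ovarian function ceases. The documents give no FSH reference range, and only the direction is used below.

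**Step 1. Who is touched by the FSH sentence.** Because F is added to A, it matters only for women who already satisfy A and are under 55. These are non-sterilised women over 45 and under 55 with a year of amenorrhea and no other cause identified. A woman who still menstruates fails A and remains of childbearing potential whatever her FSH.

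**Step 2. Natural reading: postmenopausal women are exempt.** For a woman in that group, postmenopausal = A and F.

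| FSH (mIU/ml) | F met? | Status as written | Contraception and pregnancy tests | Does FSH support menopause? |
|---|---|---|---|---|
| Below 40 | Yes | Postmenopausal | Waived | Less |
| 40 or above | No | Of childbearing potential | Required | More |

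The last two columns run opposite to each other. Within this group the classification by FSH is reversed.

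**Step 3. Literal reading of the *or*.** Taken word for word, a woman is of childbearing potential if she is not sterilised, or if she is not postmenopausal. Every non-sterilised woman past menarche meets the first half, so none is exempt and FSH is irrelevant for her. A sterilised woman who is not yet postmenopausal meets the second half and would also be covered, although sterilisation is named as a ground for exemption. On this reading the menopause and FSH sentences would exempt no non-sterilised woman. That is unlikely to be what was meant, but the words allow it.

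**Step 4. FSH sentence as a free-standing entry rule.** The sentence sits in an inclusion criterion and is phrased as a requirement. Read alone, it would bar women under 55 with FSH of 40 or above from the trial. The protocol gives no reason for such a bar, and the position of the sentence ties it to menopause.

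**Step 5. Is it corrected elsewhere?** No other section restates the FSH condition. The direction is written in words, not as a symbol, so faulty text extraction is an unlikely explanation. The calendar has a row for pregnancy tests but none for FSH, and its laboratory footnotes do not mention FSH. Item 10 therefore relies on a documented value that the trial does not schedule.

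**The case against.** Four points can be made on the other side.

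1. **The group is narrow.** A reader might infer that all women under 55 with low FSH escape the safeguards, or that amenorrhea from illness, drugs or stress would pass as menopause. The documents do not support either inference. The age limit and the year of amenorrhea still apply, and amenorrhea with a recognised other cause fails the menopause sentence before FSH is considered. What remains is amenorrhea whose cause has not been recognised, which is the case an FSH check is there to catch. This limits the size of the problem but does not remove it.

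2. **The literal *or* exempts no non-sterilised woman.** This stands as a matter of wording. It cannot be said with certainty that the text removes protection from anyone. But a defence that leaves the menopause and FSH sentences without effect for these women shows a second drafting fault, and sites cannot be expected to apply it uniformly.

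3. **Other provisions deal with pregnancy.** Sections 6.3 and 11.1.5 require discontinuation of study drug if a subject becomes pregnant, and Section 11.1.5 requires reporting, whatever her earlier classification. These act after exposure and do not replace testing and contraception beforehand.

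4. **No statistical result is affected.** This is correct. No endpoint, sample size, power figure or analysis set depends on the FSH sentence. The point concerns participant safety and the clarity of eligibility.

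**Conclusion.** The concern holds within stated limits. The FSH condition points in the opposite direction to the menopause definition it supplements, nothing else in the protocol corrects it, and the definition controls contraception and every protocol-required pregnancy test, including the one at crossover to Part B. On the natural reading it conflicts with the caution called for by the protocol's own non-clinical data.

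The documents do not say how many women fall in the affected group; it is probably small. The conclusion rests on two assumptions: that FSH rises when ovarian function ceases, and that postmenopausal women are meant to be exempt. If the literal *or* governed instead, no non-sterilised woman would be released, and the fault would be an unclear rule and not a reversed one. The text needs repair under either reading.

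A reader might also infer that changing one word settles the matter because FSH testing is already in the plan. The documents do not support that: the *or* would remain unresolved, and the calendar lists no FSH test.

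**What to change.** - **Item 10, FSH sentence.** The sponsor should reconcile the direction of the FSH condition with the menopause definition it follows. The choice of cut-off is a clinical decision for the sponsor, and none is proposed here.
- **Item 10, childbearing-potential sentence.** Reword the *or* so that it is clear whether sterilised women, postmenopausal women, or both are exempt.
- **Section 7.** Reconcile item 10 with the study calendar and its laboratory footnotes, so that sites know where the documented FSH value is to come from.
- **Sites.** Send a memo explaining the correction, and ask sites to review any woman under 55 classed as postmenopausal under the current wording, for Part A and for crossover to Part B.

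The cost is a short text amendment and a site memo. Sample size, analyses and timelines for the statistical work are unchanged. Whether the calendar needs an FSH entry depends on how the sponsor resolves the third item.

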3.2 Exclusion Criteria

1. Patients are excluded if they have active brain metastases or leptomeningeal metastases. Subjects with brain metastases are eligible if metastases have been treated and there is no magnetic resonance imaging (MRI) evidence of progression for at least 2 weeks after treatment is complete and within 28 days prior to the first dose of nivolumab administration. There must also be no requirement for immunosuppressive doses of systemic corticosteroids (> 10 mg/day prednisone equivalents) for at least 2 weeks prior to study drug administration.
2. Patients with controlled brain metastases are allowed on protocol if they had brain metastases that were surgically resected without recurrence and/or up to 3 metastases treated with SRS without progression on MRI obtained at least 2 weeks after completion of radiation and within 28 days prior to initiation of nivolumab.
3. Patients should be excluded if they have an active, known or suspected autoimmune disease. Subjects are permitted to enroll if they have vitiligo, type I diabetes mellitus, residual hypothyroidism due to autoimmune condition only requiring hormone replacement, psoriasis not requiring systemic treatment, or conditions not expected to recur in the absence of an external trigger
4. Patients should be excluded if they have a condition requiring systemic treatment with either corticosteroids (> 10 mg daily prednisone equivalents) or other immunosuppressive medications within 14 days of study drug administration. Inhaled or topical steroids and adrenal replacement doses > 10 mg daily prednisone equivalents are permitted in the absence of active autoimmune disease.
5. As there is potential for hepatic toxicity with nivolumab or nivolumab/ipilimumab combinations, drugs with a predisposition to hepatotoxicity should be used with caution in patients treated with nivolumab-containing regimen.
6. Active infection requiring systemic therapy
7. Has any other medical or personal condition that, in the opinion of the site investigator, may potentially compromise the safety or compliance of the patient, or may preclude the patient's successful completion of the clinical trial.
8. Patients should be excluded if they are positive test for hepatitis B virus surface antigen (HBV sAg) or hepatitis C virus ribonucleic acid (HCV antibody) indicating acute or chronic infection
9. Patients should be excluded if they have known history of testing positive for human immunodeficiency virus (HIV) or known acquired immunodeficiency syndrome (AIDS)
10. Allergies and Adverse Drug Reaction
 - History of allergy to study drug components
 - History of severe hypersensitivity reaction to any monoclonal antibody

11. Known additional malignancies within the past 3 years (excluding basal or squamous cell skin cancers, CIS or localized prostate cancer that has been treated or is being observed)
12. Prior solid organ or stem cell transplant

3.3 Inclusion/Exclusion Criteria- Part B

1. Must meet eligibility criteria for initiation of Part A with the exception of being allowed to have prior nivolumab in Part A of this protocol.
2. Must have evidence of either RECIST 1.1 defined Disease Progression or Stable Disease 1 year after initiating nivolumab therapy
3. Tumor biopsy prior to combination treatment is mandatory. If a biopsy/resection of a new lesion or primary tumor and slow freezing of fresh tissue for single cell RNAseq study (as specified in the CLM) is not feasible, the subject is not eligible for the study. All biopsies must be core needle or excisional. Fine needle aspirate is not acceptable.
4. Must not have had a Grade ≥ 3 irAE on nivolumab monotherapy (excluding endocrine toxicity managed with replacement therapy).
5. Must not have untreated brain metastases.
6. Must not have had major surgery or radiation therapy within 14 days of starting study treatment.
7. Must not have active autoimmune disease (see protocol for exceptions).
8. Must not have a concurrent medical condition requiring use of systemic corticosteroids with prednisone >10 mg per day.
9. Must not have had prior systemic therapy for Stage IV RCC (except for nivolumab as part of part A of this protocol).

4. SUBJECT REGISTRATION

All subjects must be registered through HCRN's electronic data capture (EDC) system. A subject is considered registered when an "On Study" date is entered into the EDC system.

Subjects must be registered prior to starting protocol therapy and begin therapy **within 5 business days** of registration.

